6.2.3 Weeks 7 to 8 – Intermediate visit (Window range +/- 2 days)

Plasma samples will be collected from the subjects (control and full plasma exchange group) to allow the pertinent tests. Additional plasma samples will be collected each time for storage at -70°C and possible future assays.

The following tests will be made: biomarkers of AD (A β -40, A β -42, β -secretase, γ -secretase, cholesterol, LDL, HDL, VLDL, and C-reactive protein, rheumatoid factor, IL-1b, IL-6, ferritin, TNF- α) and plasma IgG.

During the visit medical history will be checked with the recording of any anomalies. Concomitant medication is also to be registered, together with any adverse event detected since the last visit or since the last plasma exchange session.

Central catheter will be also extracted during this intermediate visit.

After the intensive plasma exchange period (weeks 1 to 6) and before Maintenance period, lumbar puncture will be performed to assess the levels of A β -40, A β -42, P-tau, T-tau and other Alzheimer's disease biomarkers together with standard tests (cell counts, glucose, proteins and albumin). Time collection for the CSF must be between 8am and 12am.

During this intermediate visit (weeks 7 to 8) the following cognitive impairment and behavioral tests will be made: ADAS-Cog, MMSE, NPS battery, ADCS-ADL, NPI, CDR-Sb, ADCS-CGIC, CSDD and CSSRS. Likewise, anxiety and restlessness tests will be made based on the Overt Aggression Scale (OAS) and the Agitated Behavior Scale (ABS), if considered opportune.

During the study period between week 7 and 8, a FDG-PET and an MRI will be also carried out.

Control group

The control group will undergo simulated (sham) central catheter removal and will follow the same schedule of assessments as the treated groups

6.2.4 Months 3 to 14 - Maintenance Period

Treatment Groups: Maintenance Period (Plasmaphereses + albumin or IVIG) (Window range +/- 5 days)

At months 6, 9, 12 and 14, the following cognitive impairment and behavioral tests will be made: ADAS-Cog, MMSE, NPS battery, ADCS-ADL, NPI, CDR-Sb, ADCS-CGIC, CSDD, CSSRS, QoL-AD and RUD-Lite[®]. Likewise, anxiety and restlessness tests will be made based on the Overt Aggression Scale (OAS) and the Agitated Behavior Scale (ABS), whenever considered opportune.

The plasma samples of the patient will be collected before and 15-30 minutes after each procedure, to allow the pertinent tests. These plasma samples collected before and after the procedure will be stored at -70°C for possible future assays.

The following tests will be made before each procedure: biomarkers of AD (A β -40, A β -42, β -secretase, γ -secretase, cholesterol, LDL, HDL, VLDL, C-reactive protein, rheumatoid factor, IL-1b, IL-6, ferritin, TNF- α), coagulation factors (prothrombin time (Quick), aPTT, calcium and fibrinogen), and proteinogram (total proteins, albumin, α_1 -globulina, α_2 -globulina, β -globulina, γ -globulina and IgG). In addition, a cell count will be made including hematocrit, hemoglobin and erythrocytes, platelets and leukocytes (if an abnormal leukocyte count is recorded, it will be obligate to specify neutrophils, basophils, eosinophils, lymphocytes and monocytes). The samples obtained after plasma exchange will only be used to evaluate the biomarkers of AD and, if necessary, to assess coagulation factors. A more intense monitoring is not considered mandatory since in this period the procedure is similar to a plasma donation plasmapheresis. However, the investigator can decide to assess other parameters for safety reasons. Other liver or kidney biochemical markers (AST, ALT, bilirubin, LDH, creatinine and troponin), and serology (anti-HIV and HCV antibodies, and HBsAg antigen) will be also done..

There will be 3 treatment groups. A maximum of 12 plasmaphereses will be performed, one plasmapheresis per month. In the first treatment group there will be 9 plasmaphereses with infusion of albumin 20% (200 mL, 40 g) at months 4, 5, 6, 8, 9, 10, 12, 13 and 14 and 3 plasmaphereses with infusion of IVIG (20 g) at months 3, 7 and 11. In the second treatment group, the schedule will be the same as previous but with half of the dose of albumin 20% (100 ml, 20 g) and IVIG (10 g). The third treatment group will follow the same schedule but only half-dose albumin (100 ml, 20 g) will be administered in each of the 12 plasmaphereses, that is, this group will not receive IVIG. The plasma removed and the albumin infused after the procedure depends on patient's weight (see Table 1, Appendix 10).

The subject will remain in the center throughout the procedure and then for as long as needed to ensure a safe return home, under conditions similar to before the procedure.

Before each plasmapheresis, a physical examination will be made, with the recording of any anomalies. Concomitant medication is also to be registered, together with any adverse event detected since the last visit or since the last plasma exchange session.

The anxiety and restlessness tests, if necessary, will be performed before each plasmapheresis, and between 15-30 minutes after the administration of albumin or IVIG. These tests will be carried out by the same patient supervisor.

Vital signs (axillary temperature, heart and respiratory rate, and blood pressure) will be determined 15-30 minutes before plasmapheresis, during and again 15-30 minutes after the administration of albumin or IVIG and as often as considered opportune by the investigator.

Any adverse event during or after the procedure, will be recorded.

A FDG-PET will be carried out at months 9 and an MRI also will be carried out at months 6, and 9.

Control group

The control group will undergo simulated (sham) low-volume plasma exchanges but will follow the same schedule of assessments.

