6.2.6 Description of the Response Evaluation Methods

Medical history will be performed according to usual practice. Physical examination likewise will be performed according to the practice of the investigator. The investigator will carry out a general evaluation of the body systems, together with a full physical examination during the initial visit and again at the end of follow-up. The vital signs will be measured according to standard practice of the investigator.

Blood samples will be drawn according to standard practice of the center for the obtainment of blood, plasma and serum.

The amount of blood and CSF to be collected for all the tests will correspond to the amount needed for the assays in each visit or procedure. The precise amount of each sample will be established according to the requirements of the specific laboratory performing the analysis. As a recommendation, the minimum amounts are:

- Plasma samples for frozen back-up (-70°C): 10 mL of blood which, once processed, will be divided into three equal plasma aliquots in three cryopreservation tubes.
- From the plasma bag corresponding to each plasma exchange (FPE and LVPE), six samples will be obtained, with a maximum volume of two ml each, at each of the following time points: 30 minutes after starting replacement, after one hour, and at the end of the procedure. Thus, 18 plasma samples will also be obtained in each replacement session. The removed plasma bag from the FPE and LVPE will also be collected. These samples will be collected in some selected sites.
- A β and P-tau: 10 mL of blood (to obtain 5 mL of plasma) with EDTA (collection in polypropylene tubes is needed, since A β adheres to glass). In addition, 10 mL of blood with EDTAK2 will be obtained separately to assess A β in blood.
- Genetic markers: 4 mL of blood (approximately 2 mL of plasma) with EDTA.
- Coagulation parameters: 5 mL of blood (collected according to standard practice of the laboratory).
- Hematological tests: 5 mL of blood (collected according to standard practice of the laboratory).
- Proteinogram, biochemistry (kidney and liver function), and serology: 10 mL of blood (collected according to standard practice of the laboratory).

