5.2 Renal Dysfunction/Failure

Acute renal dysfunction/failure, acute tubular necrosis, proximal tubular nephropathy, osmotic nephrosis, and death have been reported in patients receiving IGIV, particularly those products containing sucrose¹. Flebogamma 5% DIF does not contain sucrose.

Ensure that patients are not volume-depleted before administering Flebogamma 5% DIF. For patients judged to be at risk for developing renal dysfunction, including patients with any degree of pre-existing renal insufficiency, diabetes mellitus, age greater than 65, volume depletion, sepsis, paraproteinemia, or patients receiving known nephrotoxic drugs, administer Flebogamma 5% DIF at the minimum dose and rate of infusion practicable¹. (see *Boxed Warning, Dosage and Administration (2.3)*) Periodic monitoring of renal function and urine output is particularly important in patients judged to be at increased risk of developing acute renal failure¹. Assess renal function, including measurement of blood urea nitrogen (BUN) and serum creatinine, before the initial infusion of Flebogamma 5% DIF and at appropriate intervals thereafter. If renal function deteriorates, consider discontinuation of the product.

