| Window Range (days) | | | | +/- 1 | +/- 1 | +/- 1 | +/- 1 | +/- 1 | +/- 1 | +/- 2 | +/- 5 | +/- 5 | +/- 5 | +/- 5 | +/- 5 | +/- 5 | +/- 5 | +/- 5 | +/- 5 | +/- 5 | +/- 5 | +/- 5 | +/- 2 | |
| Months | -1 | | | 1 | | | | 2 | | | 3 | 4 | 5 | 6 | 7 | 8 | 9 | 10 | 11 | 12 | 13 | 14 | 14 | |
| Laboratory Tests | | | | | | | | | | | | | | | | | | | | | | | | |
| Blood cell counts | X | | | B+A | B+A | B+A | B+A | B+A | B+A | | B | B | B | B | B | B | B | B | B | B | B | B | B | X |
| Platelet counts | X | | | B+A | B+A | B+A | B+A | B+A | B+A | | B | B | B | B | B | B | B | B | B | B | B | B | B | X |
| Prothrombin time (Quick) | X | | | B+A | B+A | B+A | B+A | B+A | B+A | | B(X) + A(O) | B(X) + A(O) | B(X) + A(O) | B(X) + A(O) | B(X) + A(O) | B(X) + A(O) | B(X) + A(O) | B(X) + A(O) | B(X) + A(O) | B(X) + A(O) | B(X) + A(O) | B(X) + A(O) | X | |
| aPTT | X | | | B+A | B+A | B+A | B+A | B+A | B+A | | B(X) + A(O) | B(X) + A(O) | B(X) + A(O) | B(X) + A(O) | B(X) + A(O) | B(X) + A(O) | B(X) + A(O) | B(X) + A(O) | B(X) + A(O) | B(X) + A(O) | B(X) + A(O) | B(X) + A(O) | X | |
| Fibrinogen | X | | | B+A | B+A | B+A | B+A | B+A | B+A | | B | B | B | B | B | B | B | B | B | B | B | B | B | X |
| Proteinogram | X | | | B+A | B+A | B+A | B+A | B+A | B+A | X | B | B | B | B | B | B | B | B | B | B | B | B | B | X |
| Plasma IgG | X | | | B+A | B+A | B+A | B+A | B+A | B+A | X | B(X) + A(O) | B(X) + A(O) | B(X) + A(O) | B(X) + A(O) | B(X) + A(O) | B(X) + A(O) | B(X) + A(O) | B(X) + A(O) | B(X) + A(O) | B(X) + A(O) | B(X) + A(O) | B(X) + A(O) | X | |
| Calcium | X | | | B+A | B+A | B+A | B+A | B+A | B+A | | B(X) + A(O) | B(X) + A(O) | B(X) + A(O) | B(X) + A(O) | B(X) + A(O) | B(X) + A(O) | B(X) + A(O) | B(X) + A(O) | B(X) + A(O) | B(X) + A(O) | B(X) + A(O) | B(X) + A(O) | X | |
| AST | X | | | A | A | A | A | A | A | | | | | | | | | | | | | | | X |
| ALT | X | | | A | A | A | A | A | A | | | | | | | | | | | | | | | X |
| Bilirubin | X | | | | | | | | | | | | | | | | | | | | | | | X |
| LDH | X | | | A | A | A | A | A | A | | | | | | | | | | | | | | | X |
| Creatinine | X | | | A | A | A | A | A | A | | | | | | | | | | | | | | | X |
| Troponin * | X | | | A | A | A | A | A | A | | | | | | | | | | | | | | | X |
| Anti-HIV | X | | | | | | | | | | | | | | | | | | | | | | | X |
| HCV antibodies | X | | | | | | | | | | | | | | | | | | | | | | | X |
| HBsV Ag | X | | | | | | | | | | | | | | | | | | | | | | | X |

FPE: Full Plasma Exchange

LVPE: Low-Volume Plasma Exchange

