control patients. However, according to Version 1.0, laboratory values have only been assessed at Baseline, the intermediate visit, LVPE4, LVPE7, LVPE10, and the final Visit. The data from all protocols will be combined for the final analysis wherever possible. These study patients treated under protocol Version 1.0 will be combined to the treatment groups from protocol Version 2.0 or later versions of the protocol as follows:

- Treatment arm A: (100% albumin+Flebo V1.0) + (100% albumin+Flebo V2.0)
- Treatment arm B: (1/2 albumin+Flebo V1.0) + (1/3 albumin+Flebo V1.0) + (1/2 albumin+Flebo V2.0)
- Treatment arm C: (1/2 albumin V2.0)
- Treatment arm D (no treatment): (Control V1.0) + (Sham V2.0)

where V2.0 is protocol Version 2.0 or later versions.

A sample size of 312 subjects (78 per each of the 4 groups) will make it possible to detect with nearly 92% power for the first of the co-primary efficacy variables (the changes from baseline of the ADAS Cog scores) a difference in the mean of 3 points between any of the treatment groups and the control group, assuming the common standard deviation (SD) to be 5.55 (according to the data obtained in the phase II study), with a level of significance of 5%. This same sample size provides over 98% power for second of the co-primary end point variables (the changes from baseline of the ADCS-ADL scores) a difference in the mean of 6.69 points between any of the treatment groups and the control group, assuming the common standard deviation (SD) to be 10.0 (according to the data obtained in the phase II study), with a level of significance of 5%.

The study will have joint power for these co-primary end points of at least 90% ($0.92 \times 0.98 = 0.90$). The calculation makes the conservative assumption that these end points are independent. Since these end points are positively correlated 90% should serve as a lower bound on power.

Assuming a global dropout rate of approximately 15%, the study would have to enroll 364 subjects to obtain 312 subjects for evaluation.

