7.2.1 Plasma Exchange

The percentage of plasma exchanges (full and low volume exchanges, including the infusion of albumin and IVIG) associated with at least one adverse event that may be related to the study procedure (adverse reactions) will be summarized. Only adverse events with an onset no later than 72 hours after the end of the plasma exchanges (including the infusion of albumin or IVIG) will be considered for this analysis.

Plasma exchanges (full and low volumes exchanges) will also be summarized by the following measures:

- Plasma exchange performed (yes/no)
- Duration of plasma exchange
- Plasma exchange completed (yes/no)

The reasons for not completing the plasma exchanges will be presented in a data listing.

For the full plasma exchanges, also the following measures will be summarized:

- Route to perform full plasma exchange (peripheral / central)
- Number of bottles of albumin used (calculated as numbers of bottles in this batch + all additional bottles).
- Plasma volume exchanged (ml)

	Title: Statistical Analysis Plan
	Project #: IG1002 AMBAR
	Version: Final 1.0 Effective Date: 31July2018
	Protocol Version: Version 5.0 Effective Date: Feb2018

- Volume RF infused (ml)

For the low volume plasma exchange, the following parameters will be summarized:

- Target plasma volume
- Target RF volume
- Type of RF used (20% HAS, Other)
- RF infused
- Plasma volume exchanged (calculated as $[(PPP_{\text{post weight}} - PPP_{\text{bag empty}}) / 1.027 \text{ g/ml}] \text{ ml}$ where $PPP_{\text{bag empty}} = 41.87\text{g}$)
- Number of bottles Albumin used

For the plasma exchange visits where IVIG are to be infused (1st and 2nd treatment arm, LVPE1, LVPE5, and LVPE9) the following parameters regarding the IVIG dosing will be summarized:

- IVIG infused (yes/no)
- Theoretical IVIG dose (g)
- Infused dose(g)
- Ratio infused dose /theoretical dose
- Number of bottles used

In addition, percentage of plasma exchanges associated with at least one adverse event will also be summarized whether or not related to the procedure and/or study drug.

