7.2.4 Clinical Laboratory Tests

Summary statistics for biochemistry, proteinogram, hematology, and clotting laboratory tests will be presented at each visit. Actual values and changes from baseline to each visit will be summarized using descriptive statistics. All changes will be changes from the baseline value, there will be no comparisons in the values between the pre- and post FPE values. Maximal shifts from baseline during the FPE and during the LVPE will be summarized using the CTC AE grading system Version 4.03 and patient counts. Shifts for laboratory values which have no CTC AE grade will be based on the normal ranges (below, within, and above the normal range, if applicable).

	Title: Statistical Analysis Plan
	Project #: IG1002 AMBAR
	Version: Final 1.0 Effective Date: 31July2018
	Protocol Version: Version 5.0 Effective Date: Feb2018

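### Section 6.2.4 requires liver, kidney, troponin and serology tests in maintenance, but Appendix 8 schedules none at LVPE1–LVPE12, so no creatinine is scheduled from week 6 to week 54–55

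*Protocol*

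**What the plan says.** Protocol section 6.2.4, covering Months 3 to 14, first lists tests taken before each procedure. It then says that more intensive monitoring is not mandatory because the procedure resembles plasma donation, and lets the investigator add parameters for safety. It closes by stating, without condition, that a further group is also carried out: "Other liver or kidney biochemical markers (AST, ALT, bilirubin, LDH, creatinine and troponin), and serology". No visit or frequency is attached to that group.

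The laboratory table in Appendix 8 reads differently. Its creatinine row begins "Creatinine | X | | | A | A | A | A | A | A": screening, then after each of FPE1–FPE6. The intermediate visit and all twelve LVPE columns are blank, and the only later entry is the final visit.

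IVIG is given at LVPE1, LVPE5 and LVPE9 in arms 1 and 2 (SAP 7.2.1: "1st and 2nd treatment arm, LVPE1, LVPE5, and LVPE9"). The Flebogamma label in Appendix 2 (its section 5.2) asks for renal function, including serum creatinine, "before the initial infusion of Flebogamma 5% DIF and at appropriate intervals thereafter".

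SAP 7.2.4 plans by-visit biochemistry summaries and adds: "Maximal shifts from baseline during the FPE and during the LVPE will be summarized using the CTC AE grading system Version 4.03".

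**The concern.** The text and the schedule cannot both be followed. A site that plans visits from the table takes no renal or liver value across three IVIG infusions. The protocol's own list of expected events (9.1.3) includes raised creatinine and acute renal failure with immunoglobulin. The label names age over 65, any pre-existing renal insufficiency and volume depletion as risk factors. The trial enrols ages 55–85, excludes only creatinine above 2 mg/dL, and gives IVIG after plasma removal of about 690–880 mL. The saline guidance in Appendix 10 applies only to the albumin sessions.

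There is also a data consequence. If some sites follow 6.2.4 and others follow Appendix 8, maintenance biochemistry is collected unevenly. Under Appendix 8 alone, the LVPE-period shift tables for these analytes would rest on unscheduled tests, which tend to be triggered by clinical concern. The 18 Version 1.0 patients might add a few values. SAP 2.1 says of them that "laboratory values have only been assessed at Baseline, the intermediate visit, LVPE4, LVPE7, LVPE10, and the final Visit", without naming the analytes.

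**Working it through.** No power, sample-size or alpha figure is involved. The check sets text against table and then counts weeks.

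**Inputs.** Analytes: section 6.2.4. Entries and weeks: Appendix 8 (FPE6 = week 6; intermediate visit = weeks 7–8; LVPE1, LVPE5, LVPE9 = weeks 9, 25, 41; LVPE12 = week 53; final visit = weeks 54–55). Enrolment 364, allocated 1:1:1:1, with 78 evaluable per arm: section 4.3 and the synopsis.

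**Entries in the Appendix 8 laboratory table.**

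| Rows | Screening | FPE1–6 | Intermediate | LVPE1–12 | Final |
|---|---|---|---|---|---|
| Creatinine, AST, ALT, LDH, troponin | yes | after each | none | none | yes |
| Bilirubin, anti-HIV, HCV antibodies, hepatitis B antigen | yes | none | none | none | yes |
| Cell counts, platelets, fibrinogen, proteinogram | yes | before and after | proteinogram only | before each | yes |
| Prothrombin time, aPTT, calcium, IgG | yes | before and after | IgG only | before each, after if needed | yes |

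The last two lines show that the LVPE columns are in use, and that a code for optional tests exists and is applied there. The blanks in the first two lines are therefore real omissions. In the text copy of the table, the closing entry of these nine rows falls one cell to the right of the Final header. I read it as the final visit, because section 6.2.5 lists the same analytes for that visit.

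**Could the 6.2.4 sentence mean another visit?** The final visit has its own list in 6.2.5. The intermediate visit (6.2.3) lists only AD biomarkers and plasma IgG as blood tests. Neither explains the sentence.

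**Size.**
- Blank cells: 9 rows × 12 visits = 108.
- Scheduled creatinine values: 1 screening + 6 post-FPE = 7 before LVPE1; 0 at LVPE1–LVPE12; 1 at the final visit.
- Creatinine gap: 54 − 6 = 48 to 55 − 6 = 49 weeks.
- First IVIG to next scheduled value: 54 − 9 = 45 to 55 − 9 = 46 weeks.
- Last IVIG to next scheduled value: 54 − 41 = 13 to 55 − 41 = 14 weeks.
- Patients planned for IVIG: 2 × (364 / 4) = 182. Infusions with no dropout: 182 × 3 = 546. Counting only the 78 evaluable per arm: 2 × 78 × 3 = 468.
- Bilirubin and the three serology rows: no entry from screening to the final visit.

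**With creatinine at LVPE1, LVPE5 and LVPE9.** The gaps become 9 − 6 = 3, 25 − 9 = 16, 41 − 25 = 16 and 13–14 weeks. The longest falls from 48–49 to 16 weeks.

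**The case against.** The strongest reply is that the protocol body does require these tests, that no rule makes an appendix table override it, and that the closing sentence of 6.2.4 can be read as applying at the same procedures as the tests before it. The long gap then exists only for a site that works from the table. That is fair, and the gap is stated here as a property of the Appendix 8 schedule. It does not remove the conflict, because the sentence still fixes no visit.

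The label point can also be softened. Appropriate intervals is not a number. Section 5.1.3 tells sites to infuse Flebogamma according to the prescribing information, and the investigator may add tests. The check before the first infusion is met by screening and the six post-FPE values. Exposure is also lower than labelled: at an assumed 70 kg, 10–20 g is about 143–286 mg/kg every four months, against 300–600 mg/kg every 3–4 weeks. All of this lowers the expected risk. None of it sets a visit or yields the planned LVPE-period data.

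The laboratory safety variables named in SAP 7.2 and protocol 6.1.3 do not include creatinine or liver enzymes, and those that are named do have LVPE entries. Most of the SAP 7.2.4 output is therefore unaffected. The loss is confined to renal and liver biochemistry and troponin, the last of which protocol 8.3 does list.

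Finally, samples before LVPE5 and LVPE9 come 16 weeks after the preceding infusion and would not catch an acute rise. That is correct, and it is a reason to go beyond the minimum. The pre-infusion values still inform the label's instruction to consider stopping if renal function deteriorates.

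**Conclusion.** The concern holds. Section 6.2.4 and Appendix 8 contradict each other for nine laboratory rows. On the Appendix 8 schedule, creatinine is not measured for 48–49 weeks, a period containing every IVIG infusion in arms 1 and 2: about 182 planned patients and between 468 and 546 infusions, depending on dropout. The size assumes that sites schedule from the table. A site that runs the tests under 6.2.4 would have a smaller gap, of unknown length. This is a matter of safety monitoring and completeness of safety data, and it should be corrected. It does not touch the efficacy endpoints, sample size or type I error.

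**What to change.** Amend Appendix 8 to match 6.2.4. Enter pre-procedure creatinine, AST, ALT, bilirubin and LDH at the LVPE visits, at minimum LVPE1, LVPE5 and LVPE9. Adding LVPE2, LVPE6 and LVPE10 would give a value four weeks after each infusion and is worth considering. Name in 6.2.4 the visits for troponin and serology, and enter the same visits in the table. If serology is taken after IVIG, note the label's warning (Appendix 2, section 5.11) that passively transferred antibodies can give misleading positives.

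Apply the schedule in all four arms. Section 6.2.4 already says of the controls: "The control group will undergo simulated (sham) low-volume plasma exchanges but will follow the same schedule of assessments". Identical sampling keeps the blind intact.

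The cost is a table correction and one sentence. The three-visit minimum adds up to 3 × 364 = 1,092 routine panels and the work of reviewing them. No extra draw is needed for the biochemistry or serology, because section 6.2.6 puts them on one sample, "Proteinogram, biochemistry (kidney and liver function), and serology: 10 mL of blood", and the proteinogram is already taken before each LVPE. Troponin goes to a central laboratory and would be costed separately.

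If the sponsor intended no such tests in maintenance, the sentence in 6.2.4 should be removed and the omission justified against the label. If the LVPE visits are already complete, the SAP or report should state which of these analytes have LVPE data, from which visits and how many patients.
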